Last but not the least, buccal plate thickness seems to be a determining factor for the stability of its overlying soft tissue. A thicker buccal plate might resist bone resorption more effectively.¹⁴ Furthermore, it is suggested at least 2 mm

thick crestal bone might be necessary for a stable dimension of facial mucosa.¹⁵ Unpredictable bone remodeling after immediate implant placement, especially in situations where there is a buccal wall defect, might be one of the reasons for seeing advanced soft tissue recession.¹⁶

Immediate implant restoration (IIR) is defined when an implant is restored within 48 hours after implant placement.¹⁷ With adequate implant primary stability, an implant can be restored immediately, however, it might be wise to leave it out of occlusion during the healing phase to allow for proper formation of osseointegration. The greatest advantage of this approach is to restore esthetics immediately. The responses of soft and hard tissues to this approach have been studied to some extent. A recent systematic review¹⁸ suggested that the timing of the restoration does not influence marginal bone level around implants. However, IIR might preserve the height of papilla¹⁹ and the level of mucosal margin.³ Therefore, IIR of immediately placed implants might improve the esthetic outcomes.

II. Objectives

The primary objective of this study is to evaluate the effect of IIR on clinical outcomes (mucosal recession and esthetics) of IIP implants, compared with the effect of DR on clinical outcomes of IIP implants. Essentially, we are testing whether a temporary crown placed right after the surgery will have better clinical outcomes than not placing one. Secondary outcomes will include radiographic marginal bone changes.

III. Treatment

A. Patient selection

Forty patients will be randomized into two experimental groups: 20 in the test group (IIR) and 20 in the control group (DR). In both groups, the hopeless tooth will be extracted atraumatically without raising a flap. The tooth is replaced by an immediately placed implant. The test implants will be restored with a provisional crown immediately, which will be replaced by a permanent crown at 4 ± 1 month (crown impression visit) after implant placement. The

control implants will be restored at 4 ± 1 month (crown impression visit) after the surgery.

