The informed consent will be checked (the purpose of checking the consent is to assure that the subject is still interested in the study and they are still eligible to be in the study which will also be another form of an AE screening) along with a review of the medical history. Impressions of the subject upper and lower jaws will be taken with alginate for preparation of study models and surgical guides. Bite registration will be taken with a silicone material. Clinical measurements will be taken, including probing depth, gingival recession, plaque index, gingival index, keratinized mucosa width, and the PES score. A standardized peri-apical film will be taken along with clinical photos. Eligible subjects will be randomly assigned to one of the two groups after V3.

Implant and bone surgery (V4)

The informed consent will be checked along with a review of the medical history. The blood pressure and heart rate will be checked before surgery. The area selected for surgery will be locally anesthetized and examined. The hopeless tooth will be extracted under local anesthesia, without raising a flap. If necessary, a small flap might be elevated to facilitate the extraction. For subjects with intact buccal plate (equal or less than 4 mm loss), an implant will be placed according to the manufacturer's protocol for both groups. The implant position follows the computerized surgical guides (Neoguide, Neobiotech, South Korea) that are designed based on the CBCT scans. The gap between the implant and socket wall will be filled with bone allografts (The tooth root dimension is most of the time larger than the implant). In cases with a small buccal wall defect, a collagen membrane will be used. The test implants will be restored immediately with a provisional crown, which will be replaced by a permanent crown. A healing abutment and collatape to contain bone grafts

will be placed for control implants but without immediate restoration during the healing period. A removable temporary denture may be provided at subject request. All surgical procedures will be performed by a periodontist. Implant stability will be assessed at the time of placement. Any adverse events such as no implant stability, etc. during the surgery will be reported. Clinical measurements will be taken including: socket-related and implant-related parameters. A standardized peri-apical radiograph will be taken, as well as clinical photos.

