(a) The dental school only does CBCTs on certain days and at certain times. For subject convenience the first CBCT may be scheduled at the pre-implant visit and the second CBCT may be scheduled at the implant uncover surgery. However, one or both, may be done at separate visits due to dental school CBCT scheduling. Additionally, for the convenience of the subject, the Screening, first CBCT Scan and Pre-implant visit can be combined on the same day.

(b) Clinical measurements consist of plaque Index, gingival Index, probing depth, recession, PES/WES, width of keratinized tissue, thickness of keratinized tissue, gingival margin level and socket- and implant-related features. Not all measurements will be made in each visit. Specific parameters for each visit will be listed in CRF.

(c) Schedule for these visits is based on a per subject need for a visit, not for every subject. Conditions that require additional care for subject safety, such as premature wound exposure and slower healing might require

additional visits and will be followed as adverse events

IV. Statistical Analysis

Sample Size

A power analysis was performed using a statistical power calculator. This study will have a sample size of 40 subjects, 20 in each of the two groups. We estimate to have 80% power (with a Type I error rate of 5%) to detect a mean difference of 0.8mm mucosal recession, with the estimated standard deviation of 0.8mm.²² This power calculation takes into account the estimated 10% of subjects drop out. A “p” value of less than 0.05 will be considered statistically significant.

Data Analysis

Mean values, standard deviations, and medians will be calculated for clinical and radiographic measurements. We will examine the univariate association of the defect size with the success of treatment using logistic regression. We will also attempt to examine the association of implant success with various combinations of clinical and radiographic parameters using multiple logistic regression, but acknowledge that we will be restricted by our sample size to at most two or three predictors in any model. Changes of the parameters over time within each group as well as differences between groups will be analyzed using the repeated measure of analysis of variance.

V. References

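### N=40 is sized on one two-group recession difference, but the repeated-measures ANOVA names no deciding contrast or visit and does not use the pre-randomisation V3 value as a covariate

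*Combined protocol and SAP*

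**What the plan says.** The Sample Size subsection claims 80% power at a 5% Type I error rate "to detect a mean difference of 0.8mm mucosal recession, with the estimated standard deviation of 0.8mm", with 20 patients per arm and an allowance for 10% dropout. It gives no visit, and it does not say whether 0.8 mm is the SD of a level or of a change.

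The Data Analysis subsection compares the arms in one sentence: changes in "parameters over time within each group as well as differences between groups will be analyzed using the repeated measure of analysis of variance". The logistic regressions beside it relate success to defect size and other predictors; they do not compare the arms. The Objectives section sets out to "evaluate the effect of IIR on clinical outcomes (mucosal recession and esthetics) of IIP implants", again without a time point.

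At V3 clinical measurements are taken, "including probing depth, gingival recession, plaque index, gingival index, keratinized mucosa width, and the PES score". The same section states: "Eligible subjects will be randomly assigned to one of the two groups after V3". For V5, V6, V10 and V11 the visit sections list mid-facial mucosal level instead. The Schedule of Events labels V4, the surgery, as baseline, although the V4 text lists only socket- and implant-related measurements. Footnote (b) names recession and gingival margin level as separate items and adds: "Specific parameters for each visit will be listed in CRF".

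**The concern.** A repeated-measures ANOVA with two groups and several visits yields at least three candidate answers to whether the arms differ: the group effect averaged over visits, the group-by-time interaction, and a contrast at one visit. They estimate different quantities and have different power. The sample size corresponds to the third, while the analysis sentence does not choose. The choice could then be made after the data are seen.

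The V3 value sharpens the problem. It precedes randomisation, so it can carry no treatment effect. Entered as one more time level, it pulls the averaged group difference towards zero. Entered as a covariate, it leaves the treatment difference intact and removes variance to the extent that it predicts the later value. The plan does not say which is meant.

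**Working it through.** **Inputs from the documents.** Difference 0.8 mm, SD 0.8 mm, alpha 0.05 (taken as two-sided), 20 per arm, 10% dropout, so 18 evaluable per arm. Candidate visits: V3, V5, V6, V10, V11.

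**Assumptions, because the documents are silent.** SD 0.8 mm at every visit; equal correlation rho of 0.3, 0.5 or 0.7 between visits; V3 recession comparable with the later mucosal level. Three time courses, each with 0.8 mm at V11:
- late: 0, 0, 0.8, 0.8 at V5, V6, V10, V11
- building: 0.2, 0.4, 0.8, 0.8
- constant: 0.8 throughout

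**1. The plan's own figure.** A two-sample t-test needs 17 per arm (80.7% power). 17/0.9 = 18.9, so 19 per arm and 38 in total, within two of 40. With 18 per arm the noncentrality is 0.8/(0.8 × √(2/18)) = 3.0 on 34 df, giving 83.0%. The stated N is consistent with one two-group comparison.

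**2. Group effect with V3 as a time level.** The estimate is the mean difference over m = 5 visits, with V3 contributing zero. Its standard error is 0.8 × √((1 + 4·rho)/5) × √(2/18). At rho = 0.5 this is 0.8 × 0.775 × 0.333 = 0.207 mm.
- late: mean (0.8 + 0.8)/5 = 0.32 mm; 0.32/0.207 = 1.55; power 32.5%
- building: 2.2/5 = 0.44 mm; 2.13; 54.4%
- constant: 3.2/5 = 0.64 mm; 3.10; 85.3%

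**3. Group-by-time test, same five visits.** Noncentrality is (18/2) × SS/(0.64 × (1 − rho)), where SS is the sum of squared deviations of the five visit differences from their mean. SS is 0.768 for late and 0.512 for both building and constant. At rho = 0.5 this gives 9 × 0.768/0.32 = 21.6 (97.1% power) and 9 × 0.512/0.32 = 14.4 (86.4%), on 4 and 136 df. If only the four post-operative visits enter and the difference is constant, SS = 0 and the rejection rate is 5%.

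**4. V11 contrast adjusted for V3 (ANCOVA).** Residual SD is 0.8 × √(1 − rho²), 0.693 mm at rho = 0.5. On 33 df, averaged over chance V3 imbalance, power is 85%, 91% and 98% for rho = 0.3, 0.5 and 0.7. It is 82% if V3 is uncorrelated with V11.

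| Test (power over rho 0.3-0.7) | Late | Building | Constant |
|---|---|---|---|
| Group effect, V3 as time level | 27-42% | 45-68% | 76-94% |
| Group effect, post-operative visits only | 38-56% | 62-83% | 91-99% |
| Group-by-time, V3 as time level | 89-99.9% | 71-98% | 71-98% |
| V11 contrast, V3 as covariate | 85-98% | 85-98% | 85-98% |

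**5. V3 as a covariate for an averaged outcome.** For the post-operative mean the residual variance is 0.64 × ((1 + 3·rho)/4 − rho²). In the building case the mean difference is 2.2/4 = 0.55 mm, and power is 89-96%. That compares with 45-68% with V3 as a time level and 62-83% with V3 left out. The gain from using V3 as a covariate is therefore not confined to V11.

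**6. A course that fades.** With 0.8 mm at V5, V6 and V10 and 0.4 mm at V11, the V11 contrast adjusted for V3 has 32-52% power. The group effect has 65-87% even with V3 as a time level.

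**The case against.** The strongest reply is that the low figures come from one reading. The sentence fits a group-by-time test or visit-wise comparisons as well as it fits the group effect, and in the late case where the group effect has 27-42% power the interaction has 89-99.9%. That stands. A reader might infer from the lowest row that the trial is underpowered; the documents do not support this, because they do not say that the group effect decides, or that V3 enters as a time level.

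A second reply is that V3 may not be the same measurement. The terms differ between visits, the schedule calls V4 baseline, and the CRF is not among the documents. If recession is defined as change from the pre-operative level, V3 recession is zero by construction and cannot serve as a covariate. This also stands, and makes the CRF check a precondition of the adjustment.

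A third is that a V11 contrast looks safe only because steps 2 to 5 fix the V11 difference at 0.8 mm. Step 6 confirms this. Both arms have a permanent crown by V11, so a fading difference is plausible. A reader might infer that V11 with adjustment is best in all circumstances; that does not follow.

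None of these replies supplies the missing contrast. Footnote (b) leaves the measurements at each visit to the CRF, not the deciding test or the primary visit.

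**Conclusion.** The point holds as a gap in specification with a better method available at almost no cost. It is not an error in the sample size: 40 patients are adequate for the comparison that was sized (83% at 18 per arm). As written, the analysis admits tests whose power for the same 0.8 mm at V11 runs from 5% to 99.9%, depending on the term, the visits entered and the time course. These figures rest on assumed correlations, time courses and a common SD. The gap itself does not, nor does the fact that a pre-randomisation value dilutes a group effect as a time level and does not as a covariate.

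The plan should be changed here, with medium confidence about how much power is at stake. How recession and esthetics are ordered or combined as primary outcomes is a separate question, and nothing here depends on it.

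**What to change.** Name one primary between-group contrast: mid-facial mucosal recession at the single visit to which the 0.8 mm refers. V11 is the natural final visit, but the sponsor should confirm it. Analyse it by ANCOVA, or by a mixed model with a contrast at that visit, with the V3 value as a covariate and not as a time level. Report the adjusted difference in mm with its 95% CI. State whether 0.8 mm is the SD of a level or of a change.

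First confirm in the CRF that V3 gingival recession is measured at the same mid-facial site as the later mucosal level. If it is not, adjust only outcomes that have a matching V3 value; PES is listed at V3.

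The cost is SAP wording and a CRF check, with no extra patients or visits. An uninformative V3 covariate costs about one point of power (83% to 82%). A V11 contrast also gives up power against the group effect averaged over visits, even with V3 among them, in two situations: a constant difference with low correlation (85% against 94% at rho = 0.3), and a difference that falls to 0.4 mm by V11 (32-52% against 65-87%). The sponsor should weigh these when naming the visit.

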Subjects who lose more than 4mm of buccal plate after extraction will be excluded from the study at this time. They will receive bone allografts and collagen membrane as a socket grafting material. The test implant that does not achieve 30 N-cm will be treated as a control implant and excluded from the study.

Post-op visits after implant and bone surgery (V5, V6, V7 if necessary)

Post-op visits will be scheduled at 14 ± 3 days, 28 ± 3 days, and varied date upon subject oral condition, if needed. The informed consent along with a review of the medical history will be checked at each visit. Clinical measurements will be taken, including: mid-facial mucosal level, papilla height and labial ridge contour. Clinical photos will be taken during the visit. The

wound will be gently debrided and disinfected. Sutures, if any, will be removed.

Additional post-op visits (V7) may be necessary for conditions that require additional care for subject safety, such as premature wound exposure, minor infection, and slower healing. They are based on per subject needs for a visit, not for every subject and will be followed as adverse events. No clinical measurements will be taken at this visit.

Management of adverse events

If the dental implant does not achieve primary stability (10-20 % of prevalence rate) due to infection or other reasons, the implant will be removed in a brief surgery. The osteotomy site will be grafted with allograft bone and covered by a collagen membrane. The wound will be closed with sutures. The participants with the abovementioned conditions will be withdrawn from the study.

Alternative treatments will be given. All adverse events will be reported.

Crown impression (V9)

The impression visit will be at 4 (+/- 1) months after the baseline surgery, depending on the healing of the bone graft and implant. The informed consent will be checked along with a review of the medical history. Any adverse events will be screened and reported. If the implant fails, it will be removed and the site will be grafted at no charge. The subjects with a failed implant will be excluded. Impressions will be taken for upper and lower jaws with alginate and silicone materials, along with a bite registration.

Crown placement (V10)

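### In its classical complete-row form, the planned repeated-measures ANOVA would drop completers lacking a V5 or V6 value from the recession analysis and leave withdrawn subjects' early values unused

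*Combined protocol and SAP*

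**What the plan says.** Section IV, Data Analysis, names one method for comparing the arms on these parameters: "differences between groups will be analyzed using the repeated measure of analysis of variance". It does not say which form of the method is meant, which visits enter, what the analysis set is, or what happens to incomplete records.

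Section IV, Sample Size, plans 20 subjects per group: "We estimate to have 80% power", "to detect a mean difference of 0.8mm mucosal recession", with an SD of 0.8 mm. On lost data it says only: "This power calculation takes into account the estimated 10% of subjects drop out".

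Section III lists mid-facial mucosal level, papilla height and labial ridge contour at the two post-op visits (V5, V6), at crown placement (V10) and at the final visit (V11). On timing: "Post-op visits will be scheduled at 14 ± 3 days, 28 ± 3 days". PES/WES is not listed at V5 or V6, and the Schedule of Events shows no radiograph there. V7 is optional and carries no clinical measurements.

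The Schedule of Events allows withdrawal for a loose implant at V5, V6, V7, V9 and V10. The V9 text adds: "The subjects with a failed implant will be excluded".

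**The concern.** Recession is part of the primary objective and is the variable on which the sample size rests. Classical repeated-measures ANOVA works on complete rows, which has two separate consequences here.

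- **Completers.** A subject with a valid V11 value but no V5 or V6 value is removed from the recession analysis. This subject has not dropped out, so a dropout allowance does not naturally cover the loss.
- **Withdrawn subjects.** A subject withdrawn at V9 or V10 has V5 and V6 values that are not used. The subject is already counted in the 10%, but the information is discarded. Complete-row analysis is also unbiased only if incomplete subjects resemble the others (missing completely at random). That is doubtful when withdrawal is triggered by the state of the implant.

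At stake are a small power reserve and a choice of missing-data handling that would otherwise be made with the data in hand.

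**Working it through.** **Inputs from Section IV, Sample Size:** difference 0.8 mm, SD 0.8 mm, so d = 0.8/0.8 = 1.0; Type I error 5%; power 80%; 20 per arm; 10% dropout. Sidedness is not stated; two-sided is assumed.

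**Step 1: reproduce the plan's figure.** Normal approximation: n = 2(1.960 + 0.842)²/1.0² = 15.7, so 16 per arm, and 16/0.9 = 17.8, so 18 after dropout. The exact noncentral t gives 17 per arm, and 17/0.9 = 18.9, so 19 per arm or 38 in total. The planned 40 agrees within two subjects. A one-sided test would need 13 per arm, 15 after dropout, which does not match.

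**Step 2: the reserve after planned dropout.** 20 × 0.9 = 18 per arm. Power comes from the noncentral t with 2n − 2 degrees of freedom and noncentrality d√(n/2).

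- n = 18: noncentrality 3.00, power 83.0%
- n = 17: power 80.7%
- n = 16: power 78.1%

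The design can lose about one completer per arm before power falls below 80%.

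**Step 3: which visits a completer can miss.** The recession measure is listed at V5, V6, V10 and V11. A completer has V11 by definition. V10 is placement of the final crown, which V11 then follows up, so a completer can hardly miss it. That leaves V5 and V6.

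**Step 4: complete rows among completers.** Let m be the proportion missing each of V5 and V6, independently. The documents give no value, so m is an assumption. Complete rows per arm = 18 × (1 − m)².

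| m (assumed) | (1 − m)² | Complete rows per arm | Total | Power |
|---|---|---|---|---|
| 0 | 1.000 | 18.0 | 36.0 | 83.0% |
| 2% | 0.960 | 17.3 | 34.6 | 81.4% |
| 3% | 0.941 | 16.9 | 33.9 | 80.5% |
| 5% | 0.903 | 16.2 | 32.5 | 78.8% |
| 10% | 0.810 | 14.6 | 29.2 | 74.0% |

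Power falls below 80% somewhere between 3% and 5% missed per visit. In every row, V11 values exist for all 36 completers.

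**Step 5: which outcomes are touched.** Only parameters recorded at V5 and V6 are affected. A missed V5 or V6 removes nothing from PES/WES or marginal bone level.

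**The case against.** **Deletion is a likely default, not a stated rule.** The wording does not exclude a mixed-model version of repeated-measures analysis. This stands, and it is why the point is limited to the classical form. Nothing in the plan calls for the other version, however.

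**The power figures are for one time point.** A between-group test that averages four visits could have more power. With a constant 0.8 mm difference and an assumed within-subject correlation ρ, the variance of the four-visit mean is (1 + 3ρ)/4 of a single value's. For ρ = 0.5 to 0.8 this makes d = 1.26 to 1.08, and at 16.2 per arm power is about 94% to 85%. This also stands if the difference is constant over visits; if it appears only late, the gain shrinks. The plan names no time point or contrast that would settle the matter. The single-time-point figures match the plan's own sample-size calculation.

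**Subjects have reason to attend.** V5 and V6 are the wound-care and suture-removal visits, so missed visits may be rare. This is fair, and the rates above are assumptions.

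A reader might also infer more than the documents support:

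- *That withdrawals exceed the 10%.* The documents do not show this. Section III, Patient selection, replaces failures up to the point where the implant is placed and deemed stable. Management of adverse events calls primary-stability failures, put at 10-20%, withdrawn. These two places must be reconciled. If such subjects were not replaced, a 20% loss would leave 16 per arm and 78.1% power, but the text does not establish that reading.
- *That a visit outside the ±3-day window is discarded.* No such rule is stated.
- *That V10 is a third visit a completer can miss.* Counting it would give 79.3% at 3% and 76.6% at 5%, but Step 3 shows why it should not be counted.
- *That a mixed model removes the bias.* It relaxes the assumption to missing at random. It does not settle how a subject whose implant failed and was removed enters the comparison.

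**Conclusion.** The point holds for the recession-type measures and for the classical complete-row form of the planned analysis. Completers lacking a V5 or V6 value would be lost beyond the 10% allowance, and early values from withdrawn subjects would go unused.

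The effect on power is modest. From 83.0%, it falls to 81.4% at 2% missed per visit, 80.5% at 3%, 78.8% at 5% and 74.0% at 10%. These figures assume a two-sided 5% test at a single time point, d = 1.0, exactly 10% dropout and independent misses at V5 and V6. The stated 80% is therefore at risk only if the miss rate is above about 3% per visit, and the documents do not say whether it will be.

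The possible bias from implant-related withdrawal is real in principle. Its size cannot be computed from the documents, and a change of model answers it only in part.

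**What to change.** In Section IV, Data Analysis, replace the repeated-measures ANOVA with a linear mixed model for repeated measures:

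- REML estimation, with arm, visit and arm-by-visit as fixed effects and Kenward-Roger degrees of freedom.
- A covariance structure stated in advance and suited to 40 subjects, for example heterogeneous compound symmetry.
- All observed post-operative values of randomised subjects up to withdrawal.
- The between-arm difference at V11 named as the contrast for recession.
- A sensitivity analysis for withdrawals due to implant failure, because the model assumes missing at random.

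This keeps the V11 values of all completers in the analysis (18 per arm, 83.0% on the plan's own assumptions) and uses the early values of withdrawn subjects. It costs a few sentences and standard software, with no new visits, data or subjects. The small downside is that the covariance structure must be chosen beforehand.

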Immediate implant placement (IIP) is becoming a prevailing treatment modality because of improvement in implant surfaces and understanding of implant healing. The propelling force for the popularity of IIP is probably from patients' desire for faster dental rehabilitation. Numerous clinical trials³⁻⁶ have proved predictability of this approach, with survival rate similar to the conventional approach, provided with prudent case selection and treatment planning. Without being satisfied by high success rate in terms of implant function, we are now striving to achieve esthetic success. IIP was supposed to preserve soft and hard tissues around the implant, but this statement failed to hold true, as suggested by preclinical⁷ as well as clinical studies.⁸ Bone and peri-implant mucosa continue to remodel after an implant is placed in a fresh socket. A recent long-term follow-up study⁹ further pointed out there might be an increased risk of continued facial mucosa recession that is associated with IIP. On the other hand, some studies¹⁻³ suggested IIP might actually reduce the amount of facial mucosa recession, especially when the implants are also immediately restored. The effect of IIP on facial soft tissues remains unsolved.

Looking into this interesting and clinically relevant issue more closely, some factors might have contributed to the controversy that was observed in the literature. First and foremost is probably the implant position. Immediately placed implant has a tendency to shift to the buccal plate because it follows the pathway with the least resistance.¹⁰ Buccally placed implants have three times the amount of mucosal recession.¹¹ Therefore, it is advisable to use a surgical guide and guide the implant in the cingulum position. Second, the tissue biotype might determine the amount of recession after implant placement. It has been long known that a thin tissue is more prone to recess.¹² Patients with a thin tissue biotype are at a higher risk for esthetic failures after receiving immediately placed implants.⁹ Surgical modifications have been proposed to overcome potential recession, e.g. connective tissue graft and a flapless surgery. Placing a connective tissue graft has increased the buccal soft tissue by 1.1mm,¹³ although its effect on recession has never been investigated.

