The final crown placement will be within several weeks from the impression. The informed consent will be checked along with a review of the medical history. Any adverse events will be screened and reported. If the implant is loose then the subject will be taken out of the study. The implant will be removed and bone placed where the implant was at no charge to the subject. Their participation in the study will be over at this time.

Clinical measurements, including PES/WES, mid-facial mucosal level, papilla height, and labial ridge contour will be taken. All components to be used will be commercially available from Neobiotech. A standardized radiograph and

intraoral photos will be taken. Multiple visits may be required to assure the quality of crowns.

Crown follow-up/Final visit (V11)

One crown follow-up visit will be scheduled at 10 (+/- 2) months after the baseline surgery. A standardized peri-apical film, clinical measurements, clinical photos and impressions/bite registration will be done. The clinical measurements include probing depth, plaque index, gingival index, keratinized mucosa width, PES/WES, mid-facial mucosal level, papilla height and labial ridge contour. The informed consent will be checked along with a review of the medical history. Any adverse events will be screened and reported.

Schedule of Events

Event	Screening	CBCT scan	Pre-implant placement	Implant and bone surgery	Post-Op visit 1	Post-Op visit 2	Additional post-Op visits (if necessary) (c)	CBCT scan	Crown impression (IP)	Crown Placement	Crown follow-up/ Final Visit
	V1	V2	V3	V4	V5	V6	V7	V8	V9	V10	V11
Timeline				Baseline (BL)	14 D (+/- 3D)	28 D (+/- 3D)	Varied		4 (+/- 1) M after BL	3+ wks after IP	10 (+/- 2) M after BL
Informed consent	SIGN		X	X	X	X	X		X	X	X
Check BP, HR	X			X							
Med history review	X		X	X	X	X	X		X	X	X
Screen for adverse events				X	X	X	X		X	X	X
Eligibility Screen	X	X		X							
Impression and bite registration			X						X		X
CBCT Scan (a)		X						X			
Clinical measurements (b)			X	X	X	X				X	X
Periapical radiograph/ (S = Standardized)	X (optional)		X (S)	X (S)						X (S)	X (S)
Clinical photographs			X	X	X	X	X			X	X
Wound disinfection & suture removal (if any)					X	X	X				
Subject withdrawn by PI		Inadequate Bone		Inadequate Bone	Implant Loose	Implant Loose	Implant Loose		Implant Loose	Implant Loose	
Temp Crown for Test Group Only				X							
Bone Allograft				X							
Control Group – Temp Denture (at subject request)				X							

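### Repeated-measures ANOVA is planned on unevenly spaced visits with nothing said about non-sphericity, so uncorrected time and group-by-time tests could run at about 7–9% instead of 5%

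*Combined protocol and SAP*

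**What the plan says.** The longitudinal analysis is specified in one sentence of section IV, Data Analysis. Changes within each group over time and "differences between groups will be analyzed using the repeated measure of analysis of variance". The sentence does not say whether the univariate or multivariate form is meant. It gives no covariance structure, check or correction for non-sphericity, or error term for comparisons at a single visit. It does not say which term (group, time, group-by-time) or which visit carries the conclusion.

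The readings come from section III:

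- V5 and V6: "Post-op visits will be scheduled at 14 ± 3 days, 28 ± 3 days".
- V10 (crown placement): at least 3 weeks after an impression at 4 ± 1 months, so about month 5.
- V11: "One crown follow-up visit will be scheduled at 10 (+/- 2) months after the baseline surgery".

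Mid-facial mucosal level, papilla height and labial ridge contour are listed at all four visits. The Introduction says of the tissue: "Bone and peri-implant mucosa continue to remodel after an implant is placed in a fresh socket".

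The Sample Size paragraph sets the error rate: a p "value of less than 0.05 will be considered statistically significant". It gives one SD, 0.8 mm, with no SD by visit and no between-visit correlation.

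**The concern.** The univariate repeated-measures F tests for time and group-by-time hold their level only under sphericity, meaning that differences between any two visits all have the same variance. Uneven spacing does not break this by itself. It breaks if readings close together are more alike than readings far apart. Here two readings are 14 days apart and the others are months apart, in tissue that the protocol describes as still changing. A correlation that falls with time is the natural expectation.

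The plan promises tests of change over time, and these are the tests that depend on sphericity. Because the sentence is silent, corrected or uncorrected p-values, and pooled or visit-specific error, could be chosen after the data are seen. With about 18 evaluable patients per arm, that choice could decide a borderline result.

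**Working it through.** **1. The plan's own figure.** The inputs are a 0.8 mm difference, SD 0.8 mm, 80% power, 5% alpha (two-sided assumed; the plan does not say) and 10% dropout.

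- Normal approximation: n = 2 × (1.960 + 0.842)² × 0.8² / 0.8² = 15.7, so 16 per arm; 16/0.9 = 17.8, so 18 per arm.
- t test: 17 per arm gives 80.7% power; 17/0.9 = 18.9, so 19 per arm, 38 in total against 40 planned.
- With 20 × 0.9 = 18 evaluable per arm, power is 83.0%.

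The sample size is in order. The rest uses 18 per arm.

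**2. Does sphericity hold?** The documents give no correlations, so these are assumed. Take reading times t = 0.46, 0.92, 5 and 10 months, SD 0.8 mm at every visit, and correlation exp(−|t₁ − t₂|/10). The variance of a difference is 2 × 0.64 × (1 − r).

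| Pair | r | Variance of difference (mm²) |
|---|---|---|
| V5–V6 | 0.955 | 0.058 |
| V6–V10 | 0.665 | 0.429 |
| V10–V11 | 0.607 | 0.504 |
| V5–V11 | 0.385 | 0.787 |

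Sphericity needs these to be equal, and they differ more than tenfold. With S the covariance matrix, k = 4 visits and C the centring matrix, ε = tr(CSC)² / [(k − 1) tr(CSC·CSC)] = 0.60, where 1 means sphericity.

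**3. Effect on the group-by-time test.** The uncorrected test has 3 and 3 × 34 = 102 df, with a 5% critical value of 2.69. Box's approximation gives its true level as P[F(3ε, 102ε) > 2.69]. With ε = 0.601 this is 8.1%. Simulation (40,000 null trials per scenario, 18 per arm, complete data) gives slightly less:

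| Assumed correlation | Visit SDs (mm) | ε | Uncorrected | Greenhouse-Geisser |
|---|---|---|---|---|
| Equal, 0.6 | all 0.8 | 1.00 | 5.1% | 4.5% |
| Equal, 0.6 | 0.4/0.5/0.7/0.8 | 0.86 | 6.0% | 4.7% |
| exp(−Δt/5) | all 0.8 | 0.66 | 7.2% | 4.7% |
| exp(−Δt/10) | all 0.8 | 0.60 | 7.7% | 4.8% |
| exp(−Δt/20) | all 0.8 | 0.57 | 7.9% | 4.9% |
| 0.8 within early and late pairs, 0.5 across | all 0.8 | 0.67 | 7.0% | 4.7% |
| 0.8 within pairs, 0.3 across | all 0.8 | 0.56 | 8.1% | 5.1% |
| 0.8 within pairs, 0.3 across | 0.2/0.3/0.6/0.8 | 0.50 | 8.8% | 5.0% |

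The multivariate test, run for the equal and exponential patterns, gives 4.9–5.2%. The uncorrected within-arm time test gives 7.0–8.8% over falling-correlation patterns like those above. The group main effect, also run for the equal and exponential patterns, stays at 4.9–5.2%.

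**4. A single-visit contrast.** Suppose the month-10 arm difference is tested on error pooled over visits. Its SE relative to the correct one is √(mean of the visit variances) / SD at V11.

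- SDs 0.65/0.70/0.75/0.80: √(2.115/4)/0.8 = 0.727/0.8 = 0.91; Type I error 7.4–7.7%.
- SDs 0.4/0.5/0.7/0.8: √(1.54/4)/0.8 = 0.620/0.8 = 0.78; about 12.8%.
- SDs all 0.8: ratio 1.00; 4.9–5.2%, also when correlation falls.
- SDs 0.9/0.9/0.8/0.7: √(2.75/4)/0.7 = 0.829/0.7 = 1.18; about 2%.

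Using month-10 data alone gives 5.0–5.4% throughout.

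**The case against.** The strongest reply is that the plan makes no wrong assumption. It names repeated-measures ANOVA, and a Greenhouse-Geisser-corrected or multivariate version fits those words and holds about 5%. This stands: the fault is under-specification. It does not remove the point, because the uncorrected version fits the same words.

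A reader might go further and infer that the month-10 recession comparison will have intervals that are too narrow. The documents do not support that, for four reasons.

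- No month-10 contrast on pooled error is named, and month 10 is not named as the primary time point.
- No visit SDs are given. Continued remodelling describes change in tissue, not growing spread between patients. Readings in healing wounds at days 14 and 28 could be at least as variable as later ones.
- The source cited for the 0.8 mm SD is titled as 1-year results. That suggests a late-visit value but does not prove it, and there is no early SD to compare it with.
- With equal SDs the contrast is unaffected, and with falling SDs the interval is too wide. Error rates above about 13% need SD to rise roughly threefold or fourfold, which nothing in the documents indicates.

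Two further limits stand. If the group main effect is what the plan means by differences between groups, its level is safe. And the four-visit figures do not carry over to the esthetic scores: the visit descriptions list the pink score at V3, V10 and V11, and the white score only at V10 and V11. With two visits, sphericity is not an issue.

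**Conclusion.** The point holds in conditional form. If the uncorrected univariate analysis is run and between-visit correlation falls with time, the group-by-time and within-arm time tests for the soft-tissue readings run at about 7–9% instead of 5%. Unequal variances are not needed for this. With equal correlation the excess is small (at most 6.0% in the cases tried) or absent. The group main effect keeps its level.

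For a single visit such as month 10, the documents support only this: the interval may be too narrow, too wide or correct, depending on how spread changes over visits and on whether pooled error is used.

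The results assume 18 per arm, four complete readings, normal data, and SDs and correlations that are not in the documents. The excess is modest. It is worth removing because the remedy costs almost nothing.

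**What to change.** Replace the last sentence of Data Analysis with text such as: *Repeated measurements will be analysed with a model that has a separate variance for each visit and a separate correlation for each pair of visits (unstructured covariance, REML, Kenward-Roger degrees of freedom). Any arm difference at a single visit will use that visit's own variance.* Four visits need 4 variances and 6 correlations, 10 parameters in all.

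If classical repeated-measures ANOVA is kept, state that the time and group-by-time tests will be Greenhouse-Geisser corrected (or the multivariate test used), and that single-visit contrasts will use visit-specific error. Either route removes the excess shown above. The same text should say which term and visit answer the primary question.

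The cost is one or two sentences and routine software, with no change in sample size. The p-values for the time tests become slightly larger. The month-10 interval may come out wider or narrower than one based on pooled error.
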